9.9 Protocol Deviations

Protocol deviation begins as soon as the survivor signs the informed consent. Deviations are defined as a departure from approved protocol schedule of events or procedures with or without IRB approval. Protocol deviations will be classified as major or minor dependent per the identifications below.

Major: A major protocol deviation is one that will have a substantive effect on the safety, rights, or well being of subjects, data integrity, or the quality of the intervention product (CT technology).

Minor: A minor protocol deviation is a deviation that does not have a substantive effect on the safety, rights, or well being of subjects, data integrity, or the quality of the intervention product (CT technology).

Below are examples of how each protocol deviation will be coded and classified:

Category	Description	Major/Minor
Eligibility Criteria	Inclusion or exclusion not met	Major
Informed Consent	Performing study related material prior to obtaining written informed consent	Major
Withdrawal or Termination	Any situation where the study treatment discontinuation criteria are met but the subject is not discontinued from the study and continues to participate	Major
Serious Adverse Event Reporting	Failure to report serious adverse events (SAEs) within 24 hours of awareness	Major
Missed Visits	Failure to attend all 5 sessions in a 7 day period of time	Minor
Out of Window Visits	Make up sessions with live instructor are not rescheduled within a 2 week timeframe	Minor

Every major or minor deviation would be carefully monitored and registered in our database. It will be used on a regular basis, starting with FPI, by the Trial Monitoring Committee (TMC) to review the protocol deviations for that reporting period.

The TMC will identify issues trending on the study. Trends that are deemed critical by the TMC will be evaluated for safety concerns.

Section 10: GENERAL CONSIDERATIONS: REGULATORY, ETHICAL, AND TRIAL OVERSIGHT

10.1 Regulatory and Ethical Considerations

This trial will be conducted in accordance with the protocol and with the following:

- Consensus ethical principles derived from international guidelines including the Declaration of Helsinki and Council for International Organisations of Medical Sciences (CIOMS) International Ethical Guidelines
- ICH Good Clinical Practice (GCP) Guidelines
- Applicable laws and regulations

Investigators' Responsibilities:

- Ensuring that the trial is conducted in accordance with the protocol, International Conference on Harmonisation Good Clinical Practice (ICH GCP) guidelines, and applicable regulatory requirements.
- Obtaining informed consent from all participants prior to their participation in the trial.
- Reporting all serious adverse events (SAEs) to the sponsor promptly and accurately.
- Ensuring the accuracy and completeness of all data collected during the trial.
- Complying with regulatory requirements for the conduct of clinical trials in their jurisdiction.
- Maintaining the confidentiality of participants' data and protecting their rights and well-being throughout the trial.

Sponsor's Responsibilities:

- Designing the trial protocol and ensuring it is scientifically sound and ethically appropriate.
- Obtaining regulatory approval to conduct the trial and ensuring ongoing compliance with regulatory requirements.
- Providing the necessary investigational product and ensuring its quality and supply throughout the trial.
- Monitoring the conduct of the trial to ensure compliance with the protocol, GCP guidelines, and regulatory requirements.
- Collecting, analyzing, and reporting trial data to regulatory authorities and other relevant stakeholders.
- Ensuring that all investigators are adequately trained and informed about their roles and responsibilities.
- Ensuring that appropriate insurance coverage is in place to protect participants and investigators.
- Addressing any safety concerns or protocol deviations promptly and appropriately.
- Ensuring that the trial is conducted in accordance with ethical principles and that participants' rights and well-being are protected.
- Providing financial support for the conduct of the trial, including funding for investigator fees, site costs, and other expenses.

10.2 Committees

The trial will establish an Trial Monitoring Committee (TMC) to oversee the safety and integrity of the trial. The TMC will consist of independent experts in relevant fields such as oncology, biostatistics, and cancer exercise specialists. Their primary role will be to review safety data at regular intervals during the trial to ensure participant safety.

Trial Monitoring Committee will perform safety assessments every 6 months. But they will meet more often if needed such as in case of increase in AEs. The Trial Monitoring Committee will be responsible for making a determination of continuing the study based upon results of the safety assessment.

10.3 Informed Consent Process

The informed consent process will include the following key elements:

- Explanation of the trial: Participants will be provided with detailed information about the purpose, procedures, risks, and potential benefits of the trial.
- Voluntary participation: Participants will be informed that their participation in the trial is entirely voluntary, and they have the right to withdraw at any time without penalty.
- Understanding: The information provided will be presented in a clear and understandable manner, ensuring that participants comprehend the nature of the trial and its implications for their health.
- Confidentiality: Participants will be assured that their personal information will be kept confidential to the extent allowed by law.
- Opportunity for questions: Participants will be given the opportunity to ask questions and seek clarification about any aspect of the trial before providing consent.

Rescreening:

- Participants can be rescreened. Refer section 5.6 for the details.
- Participants who undergo rescreening will not typically be required to complete a new informed consent process if their initial consent remains valid. However, this will be clearly stated in the protocol, and any specific circumstances requiring a new consent will be outlined.

10.4 Data Protection

- Confidentiality Measures: Personal data will be anonymized or pseudonymized whenever possible to protect participant identity. Only authorized personnel will have access to identifiable information, and strict confidentiality protocols will be followed.
- Secure Data Storage: Participant data will be stored securely in electronic databases with restricted access. The databases will be encrypted and password-protected to prevent unauthorized access.
- Limited Access: Only authorized personnel involved in the conduct of the trial will have access to participant data. Access will be granted based on predefined roles and responsibilities, and access logs will be maintained to track data access.
- Data Transfer: When transferring data between sites or to third-party vendors, encryption and secure file transfer protocols will be used to minimize the risk of interception or unauthorized access.
- Training and Awareness: All personnel handling participant data will receive training on data protection policies and procedures. Regular awareness campaigns will be conducted to reinforce the importance of data security.

In the event of a data security breach, the following steps will be taken:

- Immediate Response: Upon discovery of a breach, the responsible personnel will take immediate action to contain the breach and mitigate any potential harm.
- Notification: Relevant stakeholders, including participants, regulatory authorities, and ethics committees, will be promptly notified of the breach in accordance with applicable regulations and guidelines.
- Investigation: A thorough investigation will be conducted to determine the cause and extent of the breach. This may involve forensic analysis of systems and data logs.
- Remediation: Measures will be implemented to address the vulnerabilities that led to the breach, such as software patches, system updates, or changes to procedures.

- Documentation: A detailed report of the breach, including the cause, impact, and remedial actions taken, will be documented for regulatory compliance and future reference.

10.5 Trial Termination

Decision Rights of Sponsor or Designee to Terminate the Trial:

- The sponsor or designee may also terminate the trial if there are safety concerns, lack of efficacy, or other unforeseen circumstances that jeopardize the integrity of the trial or the safety of participants.
- The sponsor holds the decision-making power to suspend or terminate the trial based on recommendations from the Trial Monitoring Committee, IRB and PI.

Section 11: GENERAL CONSIDERATIONS: RISK MANAGEMENT AND QUALITY ASSURANCE

11.1 Quality Tolerance Limits

The purpose of this section is to identify what will trigger internal quality assurance (QA) processes to ensure continuous improvement. The Trial Monitoring Committee will provide the oversight to review the following parameters in the table. The parameter thresholds will be evaluated on a monthly basis. When these thresholds have crossed, the primary QA process employed by the committee will conduct a Root Cause Analysis (RCA). These are the following steps:

1. Collect relevant data
2. Identifying the root causes
3. Find corrective solution
4. Update protocol
5. Implement changes with appropriate change management with relevant stakeholders
6. Monitor if the corrective solution works.

Critical to Quality Factor	Parameter	Definition	Justification for Parameter	Parameter Threshold
Safety reporting	Percentage or number of immediately reportable events reported late	Percentage or number of immediately reportable events (e.g., SAEs and other events as defined in the protocol) that are reported more than 1 day after awareness of the event	A high number of late reported, immediately reportable events could impact participant safety due to lack of timely awareness of emerging safety profile	5%
Eligibility criteria	Percentage or number of randomized participants who do not meet inclusion/exclusion criteria	Percentage or number of randomized participants with Protocol Deviations in inclusion/exclusion criteria	A high number of study participants not meeting the entrance criteria could have a significant impact on interpretation of the primary endpoint and overall validity of the trial results.	5%
Intervention handling and administration	Percentage or number of participants with premature discontinuation	Percentage or number of participants who discontinued treatment before the	A high number of participants discontinuing treatment could have a significant	5%

		end of the treatment period as defined by protocol	impact on interpretation of the primary endpoint.	
Withdrawal criteria and trial participant retention	Percentage or number of participants with withdrawal of informed consent	Percentage or number of participants with withdrawal of informed consent after treatment allocation	A high number of participants withdrawing informed consent may indicate excessive survivor burden and could significantly impact collection and interpretation of the primary endpoint.	5%
Withdrawal criteria and trial participant retention	Percentage or number of lost to follow-up participants	Percentage or number of participants who are lost to follow-up (i.e., have not continued in the trial until the last planned safety assessment and have not revoked consent nor have been reached by investigator site personnel through normal	A high number of participants lost to follow-up may indicate excessive participant burden and could impact the collection and interpretation of long-term safety and efficacy data.	10%

		communication methods). These participants have not completed the trial and their status is unknown		
Procedures supporting study endpoints and data integrity	Percentage or number of study participants for whom study endpoint data was not collected	Percentage or number of study participants for whom study endpoint data was not collected; this could include inability to perform study procedure at the protocol-defined time point	A high number of study participants for whom the failure to collect study endpoint data could impact analysis and interpretation of study results	15%
Procedures supporting trial endpoints and data integrity	Percentage or number of participants with "Major" protocol deviations other than eligibility	Percentage or number of participants with protocol deviations during the trial which are not related to protocol inclusion/exclusion criteria (i.e., informed consent, trial intervention,	A high number of study participants with important protocol deviations during the trial could have a significant impact on interpretation of the primary endpoint and overall validity of the trial results. It	10%

		prohibited concomitant medication, trial procedures, safety reporting, and discontinuation)	can also impact participant safety	
Procedures supporting trial endpoints and data integrity	Percentage of participants censored in the statistical analysis because they had no bills the entire time	Percentage or number of participants who are at risk of censoring for hospital costs	High number of participants censored for primary objective analysis would translate into smaller than assumed sample size and may impact the interpretation of the efficacy results. Alternatively, final primary objective analysis would be delayed if required sample maturity is not reached within the assumed timelines	10%

Randomization	Percentage or number of randomized participants who were incorrectly stratified	Percentage or number of randomized participants who were incorrectly stratified	High number of participants who were incorrectly stratified may lead to imbalances in baseline characteristics between treatment arms, introduce biases in the data, and significantly affect the outcome of a trial	10%
---------------	---	---	--	-----

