7.3 Lost to Follow-Up

1. We will provide clear communication about the importance of follow-up visits with some incentives for participation and maintaining regular contact with participants through phone calls, emails or reminders.
2. Offer flexibility in scheduling
3. Follow up duration will be 4 weeks after a lack of response. We will re-attempt to contact the survivor after a brief 2 week pause after which we will no longer contact the survivor.

Section 8: TRIAL ASSESSMENTS AND PROCEDURES

This section outlines the comprehensive assessments and procedures deployed throughout the trial to ensure accurate, reliable data collection across all specified endpoints, emphasizing adherence to the trial's design and objectives.

Data Collection and Assessment Methods

- Claims Record: To accurately assess the financial impact of the intervention on healthcare expenditures, participants will be requested to provide Claims Records and Explanation of Benefits documentation. This comprehensive data set will

encompass costs related to hospitalization, medication, lab visits, and other relevant medical expenses.

- **Electronic Health Records (EHR):** For a detailed and objective view of medical histories, participants will be asked to access their Electronic Health Records through platforms like MyChart. This step aims to enrich the claims data with additional medical record insights with information like days of hospitalization, disease for which treatment was undertaken, whether it was an Emergency visit or not and so on.
- **Patient-Reported Outcomes:** In a complementary approach to objective data collection, participants will also self-report on various aspects including healthcare expenditures, treatment adherence (using the MMAS-8 scale), quality of life (measured by FACT-G), pain levels (assessed through the Brief Pain Inventory), sleep quality (evaluated by PROMIS), physical activity capabilities (determined by GLTEQ), and cancer progression status. Furthermore, they will report on absenteeism (detailing the number of leave days taken, including short-term or long-term disability status) and presenteeism (evaluated through work motivation and performance review scores). These self-reported metrics will be securely collected through a digital platform, aiming to supplement and validate the analysis of claims and EHR data.

Live Coaching Consistency

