8.3 Safety Assessments and Procedures

- Responsibilities
 - The Trial Monitoring Committee will oversee safety assessments and procedures throughout the trial.
- Safety Data Collection
 - Safety data will be collected through self-reported participant interviews.
 - Standardized forms and procedures will be used for consistent data collection across study sites.
- Safety Reporting and Management
 - Procedures will be in place for the timely reporting and management of safety events, including serious adverse events (SAEs) and suspected unexpected serious adverse reactions (SUSARs).
- Safety Monitoring Committee
 - The Trial Monitoring Committee will review safety data periodically, assess participant safety, and provide recommendations to the study team.
- Participant Education and Counseling
 - Participants will receive education and counseling regarding potential safety risks associated with the intervention.
 - Open communication between participants and study staff will be encouraged to facilitate early detection and reporting of safety events.
- Risk Mitigation Strategies
 - Risk mitigation strategies will be implemented to minimize potential safety risks associated with the intervention, such as user training and device monitoring.

- Adherence to safety protocols will be monitored, and interventions will be implemented to address deviations or non-compliance.
- Regulatory Compliance
 - Compliance with regulatory requirements governing safety reporting will be ensured, including adherence to Good Clinical Practice (GCP) guidelines and ICH regulations.
 - Accurate and comprehensive safety documentation will be maintained, including safety reports and investigator brochures.

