8.4 Adverse Events and Serious Adverse Events

A serious adverse event (SAE) in this trial is defined according to the following severity grades:

- Grade 1: Mild discomfort, not interrupting normal activities
- Grade 2: Moderate discomfort, interrupts normal activities but not incapacitating
- Grade 3: Severe, resulting in disability or necessitating medical consultation (SAE)
- Grade 4: Requires hospitalization (SAE)
- Grade 5: Results in death (SAE)

Only events classified as Grade 3, 4, or 5 are considered SAEs within the context of this trial

- Time Period and Frequency for Collecting SAE Information
 - Time period
 - Start: Apr 15, 2024
 - End: Oct 15, 2025
 - Frequency
 - SAEs will be documented as they are reported by participants.
- Recording of SAEs

- While prior studies suggest minimal evidence of SAEs resulting from exercise, diet, or meditation in cancer survivors, all SAEs encountered during this trial will be meticulously recorded. Participants can report SAEs directly via the app, or coaches may report on their behalf. Reports should include the severity grade, description of the event, and the participant's perspective on whether the SAE was related to trial interventions..
- Follow up of SAEs
 - All participants will continue receiving standard care from their healthcare providers. In the event of an SAE, a dedicated physician will be assigned to assess the situation, provide immediate recommendations, and categorize the cause of the SAE based on discussions with the participant. This classification will also be documented.
- Regulatory Reporting Requirements for SAEs
 - SAEs must be reported to the Institutional Review Board (IRB) within 24 hours of the event's identification. Additionally, the Sponsor will ensure prompt notification of all investigators regarding any SAEs, enabling them to inform participants about potential risks and take any necessary precautions.
- The grading of adverse events is aligned with the Common Toxicity Criteria for Adverse Events (CTCAE) standards, which detail adverse events on a scale from 1 to 5. The complete CTCAE documentation is available on the National Cancer Institute's website: [NCI CTCAE Information](#).

Section 9: STATISTICAL CONSIDERATIONS

The analysis will be conducted on all participant data at the end of 3 months, 6 months, 12 months and 18 months (ie. end of the trial).

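### Hospitalizations held in claims and EHR data are not reconciled with the SAE log, and the 5% safety-reporting limit measures only delay after awareness

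*Combined protocol and SAP*

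**What the plan says.** The quotes come from the combined protocol and SAP. The Protocol carries the same safety, records and limit text in the same sections; there cost is exploratory rather than primary, but claims and EHR data are still collected.

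- **Definition.** The grading list in Section 8.4 includes "Grade 4: Requires hospitalization (SAE"), so a hospitalization is an SAE by definition.
- **Route into the SAE log.** Section 8.4 says "SAEs will be documented as they are reported by participants" and "Participants can report SAEs directly via the app, or coaches may report on their behalf". Section 8.3 adds "Safety data will be collected through self-reported participant interviews", using standard forms. The schedules in Section 6.1 have no row for adverse events or safety interviews.
- **Limit.** Section 11.1 sets a 5% threshold on the parameter "Percentage or number of immediately reportable events reported late". It covers SAEs and other protocol-defined events "that are reported more than 1 day after awareness of the event". On frequency: "The parameter thresholds will be evaluated on a monthly basis".
- **Second source of hospitalizations.** Section 8 asks participants for claims that include hospital costs, and for EHR data giving "information like days of hospitalization, disease for which treatment was undertaken, whether it was an Emergency visit or not". Section 6.1 schedules repeated claims access, and a check of claims with the participant every 30 days through month 18, in both arms.
- **Use.** Section 9.4 compares SAE incidence between arms and treats a higher rate under the intervention as a possible safety signal. Section 9.6 lists an unacceptable adverse event rate among the criteria for stopping or adapting the trial.

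**The concern.** The trial has two separate views of the same events. The safety view depends on someone choosing, or being asked, to report. The cost view comes from records and is refreshed regularly. Nothing connects them.

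Two consequences follow. First, the 5% limit cannot warn of under-reporting, because an event must be reported before it can be reported late. Second, reporting by a coach is open in practice only to test participants, since controls have no live coach (Sections 1.1 and 4.1). Capture could therefore differ by arm, and the SAE comparison would then mix a treatment effect with a reporting effect. The final report could also show one hospitalization count under cost and another under safety, with no account of the difference.

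**Working it through.** **1. The plan's own figures.** The 5% limit is a chosen threshold with no derivation, so there is nothing to reproduce. The Section 9.7 figures used below for scale were checked instead.

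- Unplanned hospitalisations, 5 control and 4 test, stated variance 0.8, one-sided alpha 0.05, power 80%, stated size 9 per arm. Using 0.8 as an SD, the normal formula gives 2 × 0.8² × (1.645 + 0.842)² / 1² = 7.9, so 8 per arm; the t-based calculation gives 9, which matches. Used as a variance, 0.8 gives 10 (normal) or 11 (t).
- Drop-out: 102 / (1 − 0.30) = 145.7, so 146, which matches.

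The first result fits a reading of 5 and 4 as means per participant, but the table states neither unit nor period. That reading is an assumption.

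**2. What the limit can see.** Let c be the share of true hospitalizations that get reported. No value is given, so a range is assumed. The limit is late reports / reported events. If every report is on time it is 0 / reported = 0%, whatever c is. A completeness measure would be 1 − c.

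For scale, 73 × 5 + 73 × 4 = 365 + 292 = 657 unplanned hospitalizations. Among 51 + 51 completers it is 255 + 204 = 459.

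| Assumed c | Limit as written | Never reported, 1 − c | Out of 657 | Out of 459 |
|---|---|---|---|---|
| 90% | 0% | 10% | 66 | 46 |
| 75% | 0% | 25% | 164 | 115 |
| 50% | 0% | 50% | 329 | 230 |
| 25% | 0% | 75% | 493 | 344 |

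At 80% capture the missing number is 0.2 × 657 = 131. The second column needs no event rate; the last two columns rest entirely on the per-participant reading and the assumed c.

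**3. Effect on the between-arm comparison.** Observed rate ratio = true ratio × (test capture / control capture). With the planning ratio 4 / 5 = 0.80:

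| Test capture | Control capture | Capture ratio | Observed ratio |
|---|---|---|---|
| 50% | 50% | 1.00 | 0.80 |
| 62.5% | 50% | 1.25 | 1.00 |
| 80% | 50% | 1.60 | 1.28 |
| 90% | 50% | 1.80 | 1.44 |
| 90% | 75% | 1.20 | 0.96 |

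Equal under-reporting leaves the ratio unchanged and shrinks only the counts and the absolute difference. Unequal under-reporting can hide a reduction or turn it into an apparent excess. All capture values are assumed.

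**4. Whether another section closes the gap.** Section 9.4 promises to document all SAEs but names no source beyond those in Sections 8.3 and 8.4. Section 9.9 makes failure to report an SAE within 24 hours a major deviation, and Section 11.1 has a 10% limit on participants with major deviations that mentions safety reporting. The 24-hour rule also runs from awareness. No section says that a hospitalization seen in claims, EHR or claim validation counts as awareness.

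**The case against.** The strongest reply is that nothing bars record-detected events from the SAE log. Interviews on standard forms solicit events, so ascertainment is not purely spontaneous. Staff who confirm a hospital bill with a participant could well be considered aware of it, and the 24-hour rule and the major-deviation limit would then apply. The 5% limit does what its name says: it measures lateness, in line with the 24-hour rules in Sections 8.4 and 9.9.

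Much of this stands. A reader might infer that the plan excludes claims-detected events, or that the limit covers SAEs alone. The text supports neither: it is silent on the first, and the limit extends to other protocol-defined events. A reader might also infer that the claims and EHR files hold the complete set of hospitalizations. They are supplied by participants, and Section 11.2 recommends access for as little as 6 months, so they may have gaps of their own.

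What does not stand is the idea that the existing rules suffice. The interviews have no schedule. The deviation rule and its limit work only once awareness is defined for events found in records, and the documents do not define it.

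**Conclusion.** The gap is real, and it is one of data flow and definition rather than a wrong number. Following the stated route, hospitalizations already in the trial's files can be missing from the Trial Monitoring Committee's safety data and from the Section 9.4 comparison, and the 5% limit would not show it.

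The size is not known. It is tempting to read 131 to 329 missing hospitalizations (80% to 50% capture of 657) as an estimate. It is illustrative only: the capture rates are assumed, 5 and 4 carry no unit or period, and 657 takes no account of the planned 30% drop-off. Nor do the documents show that the between-arm comparison will be biased. They show that one reporting channel exists in only one arm, which makes differential capture possible; its degree is unknown. This deserves correction because the remedy uses data already collected, but it does not by itself invalidate the trial.

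**What to change.** Amend Sections 8.4, 9.4 and 11.1 as follows.

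- **Match.** At each monthly review, compare hospitalizations found in claims, EHR or claim validation with the SAE log, by the same rule in both arms. Confirm that record access is equal first: as extracted, the EHR consent row in Section 6.1 is marked at baseline only for the test arm but repeatedly for controls.
- **Assess before entering.** Send unmatched hospitalizations through the physician assessment already in Section 8.4, with a stated rule for planned admissions, and enter those that meet the protocol's SAE definition. Entering every unmatched record as an SAE would sweep in planned admissions, which Section 9.7 lists separately.
- **Define awareness.** State that detection in the records starts awareness for the late-report limit.
- **Measure completeness separately.** Track never-reported events under their own parameter. Counting them all as late would turn a timeliness measure into a completeness measure and penalize events reported promptly once found.
- **Analyse the reconciled set.** Use it for the Section 9.4 between-arm comparison and the committee's review.

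The cost is a monthly match of existing data, physician time for unmatched events, and a few sentences in three sections. SAE counts will look less favourable, and participant-supplied records may still miss events, so the report should state how complete those records were in each arm.
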